1 LIST OF ABBREVIATIONS

AE	Adverse Event
CRF	Case Report Form
CRS	Chronic Rhinosinusitis
CV	Curriculum Vitae
EC	Ethic Committee
ENT	Ear Nose and Throat
ESS	Endoscopic Sinus Surgery
FESS	Functional Endoscopic Sinus Surgery
ID	Identification
IRB	Institutional Review Board
RS	Rhinosinusitis
SAE	Serious Adverse Event
SOP	Standard Operating Procedures

2 SYNOPSIS

Protocol Number	PG-001
Protocol Title	Safety and Effectiveness Evaluation of the Peregrine™ Drivable ENT Scope for Office Endoscopy of the Paranasal Sinuses in Patients who underwent ESS
Participating Centers	Emory University, Atlanta, GA
Clinical Phase	Open, single-center, prospective
Investigational Study Device	Peregrine™ Drivable ENT Scope, by 3NT Medical
Study Procedures	
Up to 30 Patients, out of which are at least 10 samples per each of the frontal, maxillary and sphenoid sinuses, who have had prior ESS and are scheduled for nasal endoscopy in the office as part of a routine post-operative office visit or due to recurrence of symptoms, will be evaluated with Peregrine Endoscope. The patients will attend the following visits:
 
 1. Visit 1: Screening and Enrollment – as part of a regular office visit 2. Visit 2: Sinonasal endoscopy – evaluation with Peregrine and standard endoscopes 
Visits 1 and 2 can be combined into a single visit.

Study Population	Patients who have had prior ESS
Study Purpose	To assess the safety and effectiveness of Peregrine endoscope in patients in the office setting in terms of access into and visualization of the paranasal sinus anatomy, image quality, patient tolerability and clinical utility.
Study Endpoints	
Primary – Performance and Safety Endpoints:
 
 • To compare visualization success rates of the paranasal sinus anatomy by Peregrine and by a standard endoscope used in the office setting. • Device related adverse events 
Secondary – Performance Endpoints:
 
 • To assess the adequacy of the image quality of Peregrine for endoscopy procedures in the office. • To evaluate patient tolerability and pain • To evaluate the impact of extended visualization by Peregrine on clinical workflow


Study Methods of Appraisal
	
Methods:
 
During the study the subjects will be evaluated with:
 
 Mandatory – Peregrine Endoscope (the study device) Mandatory – A Standard 30° 4mm endoscope Optional – A Standard 70° 4mm endoscope Optional – A standard Flexible Endoscope 
Safety assessment
 
Safety assessment will be based upon monitoring the Adverse device events, which will be collected throughout the procedures in which Peregrine was used.
 
Performance assessment
 
 Evaluation of ability of Peregrine and the comparison endoscope (a standard 30° endoscope) to access and visualize sinus anatomy (No. of successes divided by No. of attempts): 
 Anatomic landmarks – Maxillary (ostium, anterior wall, lateral aspect, floor), Frontal (ostium, posterior wall, anterior wall, lateral recess), Sphenoid (ostium, sella, floor, lateral recess). Visualization success rates will be confirmed by direct visualization. Level of prior resection will be recorded – anterior or posterior ethmoidectomy, draf IIa, draf IIb, uncinatectomy, antrostomy, maxillectomy, sphenoidotomy, dilation Image quality – will be assessed through a yes/no statement regarding adequacy of Peregrine image quality for office endoscopy procedures, in comparison to the standard endoscope. Patient pain and tolerability will be assessed through validated VAS for both Peregrine and the comparison endoscope. Impact of Peregrine's extended visualization capability on clinical workflow will be evaluated through a series of questions regarding identification of pathology, evaluation of mucosa, change in medical management, need for additional CT scan, indication for revision surgery, etc. Peregrine ease-of-use will be evaluated through a user questionnaire. Irrigation (through Peregrine working channel) will be documented (performed/not performed), when performed.

Inclusion/Exclusion Criteria
	
Inclusion Criteria:
 
 A male or female patient who has had prior ESS and who is indicated for office endoscopy by the ENT specialist Patient age: adult (>18 years old) A patient who is able to understand the requirements of the study, is willing to comply with its instructions and schedules, and agrees to sign the informed consent 
Exclusion Criteria:

	
 1. Any medical disorder which in the investigator's judgment contraindicates the patient's participation 2. Pregnancy
Study Duration	
Per Patient: up to 1 month
 
A total of 6 months to recruit and treat up 30 patients.

Sample Size Calculations	
The performance endpoint of the study will be to demonstrate that the Peregrine Endoscope will perform comparable to or better than a Standard 30° 4mm Endoscope, where a difference of 20% or more between visualization success rates will be considered to be statistically significant. Per protocol, a sub-group analysis of each of the different sinus cavities (i.e., Frontal, Maxillary and Sphenoid) will be used for power calculation.
 
In order to maintain minimal Power 80% and Type I ($=\alpha$) error of 5% to detect minimal differences of $\pm 20\%$, a sample size of 7 samples is needed per sinus cavity. This number does not include an estimated 20-30% drop-out rate due to technical reasons unrelated to the device. Therefore, a sample size of 10 samples per each sinus cavity, and a total of 30 samples for all sinuses (total of up to 30 patients), will be recruited to the study.

Statistical Analysis Plan	
Demographic and baseline characteristics will be summarized for all subjects included in the analysis. Continuous variables will be summarized using summary statistics (mean, standard deviation, median, range combined with 95% confidence interval calculations) and categorical variables will be summarized using counts and percentages.
 
In particular, the following tests according to the parameters type are going to be performed:
 
 • Continuous parameters will be presented by the estimated value and calculation of 95% confidence intervals. In addition, the comparison will be by using the relevant Student's t-test. • Categorical parameters will be analyzed by Fisher exact test/ chi-square tests (in case of low observed frequencies). 
Tests will be two-sided in accordance to the hypothesis regarding the tested parameters, with a significance level of 0.05.

3 BACKGROUND

3.1 Nasal Endoscopy

Nasal endoscopy is a minimally invasive, diagnostic medical procedure and currently the most preferred initial method of evaluating medical problems affecting nose and sinuses such as nasal stuffiness and obstruction, sinusitis, nasal polyposis, nasal tumors, epistaxis, recurrent bouts of sneezing and rhinorrhea.

Nasal endoscopy allows a detailed examination of the nasal and sinus cavities not possible by standard examination such as anterior rhinoscopy using headlight or head mirror (1). It is more sensitive than computed tomography (CT) for the evaluation of accessible anatomy (2) and provides valuable information regarding persistent asymptomatic disease postoperatively. Most importantly, CT scan is associated with radiation exposure harmful to the patient and should be avoided if possible.

Areas visualized during endoscopy include the nasal cavity, inferior turbinate, inferior meatus, middle meatus, uncinate process, hiatus semilunaris, maxillary ostia, anterior ethmoidal bulla, nasofrontal recess, sphenoethmoidal recess, sphenoidal ostium, olfactory cleft and the nasopharynx (3)

Overall, the procedure is considered a very safe and a low-risk one (4). Occasionally, gagging, nosebleeds or coughing may occur as the endoscope is threaded through a nostril (5). Mucosal trauma and bleeding may rarely occur, particularly in susceptible patients with increased risk of bleeding, such as those receiving aspirin or other anticoagulant medications (i.e. Plavix®, Coumadin®, etc.). In addition, although not related to the endoscopic devices, adverse reactions to the topical decongestants or anesthetic provided prior to the procedure may occur prompting verification of patients' allergies prior to application.

Currently, nasal endoscopy can be performed with a flexible or rigid endoscope, typically after a topical decongestant and anesthetic are applied to the nasal mucosa. Notably, local anesthetic may not necessarily be beneficial when performing flexible nasal endoscopy, neither alone nor in combination with a vasoconstrictor. Water was suggested to be better than lubricant for Flexible Endoscope passage (6).

Reprocessing is an issue of concern, especially for Flexible Endoscope s where multiple steps were confirmed to be critical for reprocessing to be effective (7-9). High-level disinfection has been determined to be the minimum level of disinfection required, with several steps are important in all reprocessing techniques, including manual cleaning, leak testing, cleaning with an enzymatic agent, high-level disinfection, and drying with vertical storage (7).

3NT Medical Ltd. has developed the Peregrine™ Drivable ENT Scope, which offers the convenience of a single-use endoscope component coupled with performance characteristics of commercially available state-of-the-art reusable endoscopy systems. The single-use endoscope essentially removes concerns related to burdensome reprocessing techniques of a delicate tool required to achieve high-level of its disinfection.

The Peregrine Drivable ENT Scope is a minor modification to the Sinusway endoscopy system that was cleared by the FDA under K162916 and was tested and found to be safe and effective in various clinical studies.

4 OBJECTIVES

The objective of this study is to assess the safety and performance of Peregrine endoscope in patients in the office setting in terms of access and visualization of the paranasal sinus anatomy, image quality, patient tolerability and pain.

For this study, up to 30 patients who have had prior ESS and are scheduled for nasal endoscopy in the office, as part of a routine post-operative office visit or due to recurrence of symptoms, will be evaluated with Peregrine Endoscope. Access and visualization by an additional standard endoscope will be conducted and compared to Peregrine endoscope. Image quality of the Peregrine endoscope, Patient tolerability and pain, and the impact of Peregrine on clinical decision making will be evaluated.

4.1 Safety assessment

Safety assessment will be based upon monitoring the adverse device effects, which will be collected throughout the procedure.

All adverse events and serious adverse events will be reported in accordance with reviewing Ethics Committee /Institutional Review Board (IRB), FDA and Competent authority requirements.

4.2 Performance assessment

- To compare visualization success rates of the paranasal sinus anatomy by Peregrine and by standard endoscopes used in the office setting.
- To assess whether the image quality of Peregrine is adequate for endoscopy procedures in the office.
- To evaluate patient tolerability and pain.
- To evaluate Peregrine utility in clinical decision making.

4.3 Study End Points

Primary - Safety

All adverse device effects will be captured and summarized as defined in **Section-8**. Adverse device effects (type, frequency, severity) are expected to be similar to those reported in the literature for Nasal Endoscopy (section 8).

For this study, the Safety comparison with the data of Nasal Endoscopy reported in the literature will be descriptive with no statistical endpoints.

Primary – Performance

Evaluation of ability of Peregrine and the comparison endoscope to access and visualize sinus anatomy at the following landmarks:

- Maxillary (ostium, anterior wall, lateral aspect, floor)
- Frontal (ostium, posterior wall, anterior wall, lateral recess)
- Sphenoid (ostium, sella, floor, lateral recess)

Subjects will be evaluated with:

- a. Mandatory – Peregrine Endoscope (the study device)
- b. Mandatory – A Standard 30° 4mm endoscope
- c. Optional – A Standard 70° 4mm endoscope
- d. Optional – A standard Flexible Endoscope

- Visualization success rates, calculated as the No. of successes divided by the No. of attempts, will be confirmed by direct visualization.
- Representative images of the accessed anatomic landmarks will be recorded.
- Level of prior resection will be recorded – anterior or posterior ethmoidectomy, draf IIa, draf IIb, uncinatectomy, antrostomy, maxillectomy, sphenoidotomy, dilation

Secondary - Performance

- Image quality – will be assessed through a yes/no statement regarding adequacy of Peregrine image quality for office endoscopy procedures, in comparison to the comparison device.
- Patient pain and tolerability will be assessed through validated VAS for both Peregrine and the comparison endoscope.
- Impact of Peregrine's extended visualization capability on clinical workflow will be evaluated through a series of questions regarding identification of pathology, evaluation of mucosa, change in medical management, need for additional CT scan, indication for revision surgery, etc.
- Peregrine ease-of-use will be evaluated through a user questionnaire.

Other Measurement – Performance and effectiveness

- Irrigation (through Peregrine working channel) will be documented (performed/not performed), when performed.
- To evaluate nasal cavity inflammation and sinuses inflammation using Lund Mackay CT score and Lund Kennedy Endoscopic scoring, if applicable.

As learning curve, each investigator participating in the study will use Peregrine in a cadaver specimen and/or anatomic model and/or during at least 1 procedure performed in the operating room (OR) under general anesthesia. The subject treated in the OR will be included in the safety analysis but not included in the efficacy analysis

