4. Obligatory – the surgeon will then attempt to visualize the pre-defined sinus anatomy landmarks with Peregrine endoscope which will be recorded as success/failure, and an image of the anatomic landmarks visualized will be taken. Patient will be asked to score Peregrine for pain and tolerability.
5. Optional – the surgeon will have the option to attempt to visualize the pre-defined sinus anatomy landmarks with a standard 70° 4mm endoscope and/or a flexible endoscope which will be recorded as success/failure, and an image of the anatomic landmarks visualized will be taken. Patient will be asked to score the endoscope for pain and tolerability.
6. Optional - irrigation of the nasal anatomy will be performed and recorded as Done/Not Done and which sinus was irrigated.
7. The physician will answer a set of questions related to endoscope usability and utility in clinical decision making in comparison to the standard endoscope.
8. The procedure will be recorded by site's AIDA system to enable the physician to perform assessments post procedure.

- **After the procedure:**

- The patient will recover from the procedure according to center's common practice. Before the patient is dismissed, recording of AE, if any, will be performed. Patient will exit the study.

Visit 3: Telephone Follow-up visit

- Telephone Follow-up for safety assessment will be conducted by study personnel two weeks \pm 3 days following patient last study visit.
- In the absence of any on-going ADE's, the patient will exit the study and Exit Form will be completed.

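### The image-quality item puts adequacy and comparison into one Peregrine-only yes/no: a 'no' is ambiguous, and a 'yes' shows adequacy only if the unrated standard view was adequate

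*Combined protocol and SAP*

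**What the plan says.** The aim is stated without a comparator. Section 4.2 lists "To assess whether the image quality of Peregrine is adequate for endoscopy procedures in the office", and the secondary endpoints in the Synopsis read "To assess the adequacy of the image quality of Peregrine for endoscopy procedures in the office".

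The measure adds one. Section 4.3 uses a "yes/no statement regarding adequacy of Peregrine image quality for office endoscopy procedures, in comparison to the comparison device". The methods part of the Synopsis has the same construction: "adequacy of Peregrine image quality for office endoscopy procedures, in comparison to the standard endoscope".

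No section asks for an image-quality rating of the standard scope. Pain and tolerability, by contrast, are "assessed through validated VAS for both Peregrine and the comparison endoscope", and section 6.2 (steps 3 and 4) records landmark success or failure for each mandatory scope. Step 7 of section 6.2 describes the physician's questions, but does not name image quality: "The physician will answer a set of questions related to endoscope usability and utility in clinical decision making in comparison to the standard endoscope".

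The plan gives no definition of adequate, success threshold, rater or rating unit (patient, sinus or landmark) for this endpoint. The comparator also varies. The Synopsis names the 30° scope. Sections 6.1 and 7 name the 70° scope, which is optional under sections 4.3 and 6.2.

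**The concern.** The objective is absolute and the measure is partly relative. A physician looking at an image that is usable but poorer than the 30° view could properly answer either way, depending on which half of the statement carries the weight. The item therefore does not map cleanly onto the objective it serves.

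What is at stake is the reading of a secondary endpoint. A 'no' may be counted against Peregrine although the objective was met. A high 'yes' rate may be taken as parity with the standard scope although nothing about the standard scope was rated. The primary visualization and safety endpoints are not affected.

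**Working it through.** The plan states no rate, margin, power or sample size for image quality, so there is no figure to reproduce. The check is logical, with a short illustration of what the data could estimate.

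**Step 1: possible states in one patient.** Take two readings of the item. The absolute reading asks whether Peregrine's image is adequate for office use. The relative reading asks whether it is no worse than the standard scope's image.

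| State | Peregrine adequate? | Compared with standard | Absolute reading | Relative reading | 4.2 objective met? |
|---|---|---|---|---|---|
| A | yes | no worse | yes | yes | yes |
| B | yes | worse | yes | no | yes |
| C | no | no worse | no | yes | no |
| D | no | worse | no | no | no |

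**Step 2: what a 'no' can mean.** It can come from B, C or D. The objective is met in B and fails in C and D. One binary answer cannot separate them.

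**Step 3: what a 'yes' can mean.** It can come from A, B or C. The objective fails in C, where both views are poor. If the standard view was adequate in that patient, C cannot occur, because an image no worse than an adequate one is adequate. A 'yes' then means A or B, and both meet the objective. So a 'yes' supports adequacy on that condition, and the plan does not record whether the condition holds. Even then, A and B differ on the comparison, so a 'yes' does not show whether Peregrine is better, equal or somewhat worse.

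**Step 4: what can be estimated.** The plan allows up to 30 patients. The item gives one proportion, x/n. Exact (Clopper-Pearson) 95% intervals for assumed counts are:

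- 30/30: 88.4% to 100%
- 27/30: 73.5% to 97.9%

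A difference needs a second count, which is not collected. With 27/30 for Peregrine:

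- standard 24/30: (27 - 24)/30 = +10 points
- standard 27/30: (27 - 27)/30 = 0
- standard 30/30: (27 - 30)/30 = -10 points

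The Fisher and chi-square tests in section 7 have no second column for this endpoint. They also treat groups as independent, whereas both scopes are used in the same patient.

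**Step 5: what rating both scopes would give.** Adequacy for each scope plus a worse/same/better item identifies all four states. Precision stays limited: if 3 of 30 patients are discordant, all in one direction, the exact McNemar p-value is 2 × 0.5³ = 0.25.

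**The case against.** The strongest reply has four parts.

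- **The stated aim is adequacy.** If the routine scope is taken as adequate, a 'yes' supports the aim on either reading. This stands, and it limits the point. A reader might infer that neither answer can be interpreted at all, or that the endpoint cannot serve its objective. The documents do not support that: a 'yes' is informative under a reasonable but unrecorded assumption.
- **The questionnaire is not shown.** Section 4.3 describes the statement without giving its text, and the form may be clearer. This also stands as a caution. But section 4.3 and the Synopsis define the endpoint, and they carry the mixed wording.
- **A comparative judgement contains its own comparator.** The physician uses the 30° scope and then Peregrine in the same patient. Landmark success and images are kept for both, and section 6.2 adds: "The procedure will be recorded by site's AIDA system to enable the physician to perform assessments post procedure". These data bear on whether a poor view came from the patient or the optics, so it would be too strong to say the two cannot be told apart. They are still not image-quality ratings, and no such rating from the recording is specified.
- **No claim of equal image quality is planned.** This is correct, and it makes the matter one of clear measurement on a secondary endpoint.

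A reader might also try to size the problem by assuming a share of patients with usable but inferior images and subtracting it from 100%. That only returns the assumption; the documents supply no such share.

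**Conclusion.** The point holds in a limited form. The measure adds a comparison that the objective lacks. A 'no' mixes failure of the objective with success. A 'yes' shows adequacy only where the standard view was adequate, and no difference in image quality between scopes can be estimated.

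The effect on the results cannot be sized from the documents; the counts used above are illustrations. The conclusion rests on the endpoint as worded in section 4.3 and the Synopsis. It would weaken if the unseen form asks about adequacy alone, though the protocol text would then still need to match the form.

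**What to change.** In section 4.3 and the Synopsis, replace the single statement with two items, and add them to the steps in section 6.2:

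- **(a)** Image quality adequate for office endoscopy, yes/no. Record it once per patient for each mandatory scope, right after its use: the 30° scope in step 3 and Peregrine in step 4.
- **(b)** Peregrine image compared with the 30° scope: worse, same or better. Record it once, after step 4.

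Report (a) for Peregrine with an exact 95% CI as the endpoint for the section 4.2 objective. Show (a) for the 30° scope beside it as paired descriptive data, and report (b) descriptively. Reconcile the comparator across the Synopsis and sections 4.3, 6.1 and 7.

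The cost is three answers in place of one, so two extra tick boxes per patient, by the same physician at the same visit and with no added procedure. With up to 30 patients the paired comparison will be imprecise, so the report should make no equivalence claim from it.

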5 DESCRIPTION OF PATIENT POPULATION

5.1 Patient Selection

Patients who have had prior ESS and are indicated for nasal endoscopy in the office (as part of a routine post-operative office visit or due to recurrence of symptoms)

5.2 Subject Enrollment

- a) Patients who appear to be eligible will be asked if they would like to participate in this study.
- b) Written informed consent will be obtained from each participating patient prior to collecting a patient history or other testing. The patient will be counseled concerning the research nature of this study, and the risks and possible benefits to participation. Participation is fully voluntary.

